5.5 Method of Assigning Subjects to Treatment Group

Once the subject has provided an informed consent and meets all the inclusion criteria and none of the exclusion criteria, the study site will request the study drug assignment using the Interactive Web Response System (IWRS).

All randomized subjects will be managed by IWRS. To randomize a subject, the study site will access the IWRS interlocking with electronic data capture system. The subject identifying information (e.g. gender, year of birth and/or date of birth) and the stratification factors are provided to gain the randomization number and investigational product allocation. Randomization information which includes randomization ID, regime name, regime ratio, date and time of randomization, and stratum name generated by IWRS will be delivered to the Sponsor.

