8.1 Determination of Sample Size

Randomization will be stratified by flu vaccination history within a year (Yes vs No) and participation in PK sub-study (Yes vs No).

This study is designed to obtain effect sizes of 2 different CT-P27 treatment groups and placebo group based on the time from the administration of study drug to resolution of influenza symptoms and fever.

For this proof-of-concept dose-ranging study, assuming 90% of subjects are included in the eligible infected population, the total eligible sample size of 164 (63 eligible infected subjects per CT-P27 treatment groups and 38 subjects in placebo group) achieves 80% power to detect 1.8 days of reduction for the primary endpoint of time to resolution with 5% two-sided significance level and standard deviation (SD) of 3 days using a Wilcoxon's rank-sum test.

Considering a dropout rate of 10%, this study will need 183 subjects to be enrolled to achieve 164 evaluable subjects.

For an effect size of 1.5 days of reduction in time to resolution with SD of 2.9 days, the total sample size could be increased to about 250 to achieve at least 80% statistical power with 5% two-sided significance level.

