8.5 Statistical Analyses

8.5.1 Primary Efficacy Analysis

The primary efficacy endpoint analysis will assess the time (in days) from the administration of study drug to resolution of influenza symptoms and fever. This analysis will be performed on the ITTI population. Data will be obtained from responses recorded on the Flu-iiQ™.

Resolution of symptoms has occurred if the following influenza symptoms (as recorded on the Flu-iiQ™) are mild in intensity or none for at least 24 hours.

- Respiratory symptoms (cough, sore throat, and nasal congestion).
- Constitutional symptoms (headache, feeling feverish, body aches and pains, and fatigue).

Resolution of fever is defined as:

- Body temperature of $<37.0^{\circ}\text{C}$ for at least 24 hours. (The start time for resolution of fever is defined as the time recorded in the diary when body temperature was $<37.0^{\circ}\text{C}$ for at least 24 hours.)

If the subject has received the drugs for symptom relief, the effective duration of the drugs for symptom relief should be considered.

For example, the study drug was administered at 12:00 on 1st day. The first time body temperature recorded $<37.0^{\circ}\text{C}$ in the diary was 10:00 on 2nd day and continued more than 24 hours. But acetaminophen/paracetamol known to be effective for 6 hours had been administered at 09:00 on 2nd day [1 hour prior to the time when the body temperature decreased $<37.0^{\circ}\text{C}$], it will be calculated that the start time point for body temperature $<37.0^{\circ}\text{C}$ is 15:00 on 2nd day [27 hours after the study drug administration]. Then, if the next first time body temperature recorded $<37.0^{\circ}\text{C}$ in the diary was 22:00 on 2nd day and body temperature was $<37.0^{\circ}\text{C}$ for 24 hours from then, the start time for resolution of fever is 22:00 on 2nd day [34 hours after the study drug administration].

The primary efficacy endpoint will be analyzed using a Wilcoxon rank-sum test to assess differences between treatment groups, if every subject were followed until resolution of influenza symptoms and fever. The statistically significant difference of time to resolution of influenza symptoms and fever between placebo and CT-P27 based on Wilcoxon rank-sum test will be presented by p-values. If there is any censoring, the primary efficacy endpoint will be analyzed using Log-rank test, and Kaplan-Meier plots will be presented.

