3.3 Exploratory Endpoints

- PK profiles:
 - $AUC_{0-\infty}$: Area under the concentration-time curve in serum from time zero extrapolated to infinite time
 - AUC_{0-last} : Area under the concentration-time curve from time zero to the last quantifiable concentration
 - C_{max} : Maximum observed serum concentration
 - t_{max} : Time of maximum concentration
 - C_{last} : Last observed quantifiable concentration
 - λ_z : Apparent terminal elimination rate constant
 - $t_{1/2}$: Apparent terminal elimination half-life
 - MRT : Mean residence time
 - CL : Systemic clearance from serum after IV dosing
 - V_z : Apparent volume of distribution during the terminal elimination phase after IV dosing
- Immunogenicity analysis:
 - Anti-drug specific antibodies and neutralizing antibodies for CT-P27 component antibodies (CT-P22 and CT-P23)
- HI antibody
- Genotype and phenotype of isolated influenza virus

4. Randomization, Stratification and Blinding

Subjects will be randomly assigned to a treatment group after they provide an ICF and meet all the inclusion criteria and none of the exclusion criteria by using Interactive Web Response System (IWRS). The randomization will be stratified by flu vaccination history within a year (Yes vs No) and participation in PK sub-study (Yes vs No).

This study will be double-blinded. The study blind will not be broken except in a medical emergency (where knowledge of the investigational medicinal product administered would affect the treatment of the emergency) or regulatory requirement (e.g., for Serious Adverse Event (SAE) or death). If the blind is broken, the date, time, and reason must be recorded in the subject's eCRF and any associated AE report.

The database will be unblinded to unblind person predefined by the sponsor [REDACTED]. However, the study will remain blinded to the investigators and subjects until study termination.

Statistical Analysis Plan

5. General Statistical Considerations

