The primary efficacy endpoint will be analyzed using a Wilcoxon rank-sum test to assess differences between treatment groups (CT-P27 45 mg/kg vs placebo, CT-P27 90 mg/kg vs placebo), if every subject is followed until resolution of influenza symptoms and fever. The Wilcoxon rank-sum test will be used to test for a statistical significant difference of time to resolution between placebo and CT-P27. The results of the analysis will be summarized using p-values. The significant level will be set to 5%. If p-value is lower than 5%, it is considered that there is a significant difference between placebo and CT-P27. For subjects who withdrew from the study before the symptoms have resolved or if the symptoms did not resolve until the data cut-off, data will be censored at the latest date/time recorded on the diary or start date/time of study drug administration when there are no recorded data on the diary after study drug administration. If there is any censoring, the primary efficacy endpoint will be analyzed using Log-rank test and Gehans Wilcoxon test, and the result will be presented by p-values from the two tests. Also the table will present count of censoring reasons and 25th percentile, median, 75th percentile of time from administration of study drug to resolution. Kaplan-Meier plots will be presented.

CONFIDENTIAL

Statistical Analysis Plan

If there are no censoring data, sensitivity analysis using tipping point analysis under Missing Not at Random (MNAR) will be also performed to explain varying cases about average unobserved outcomes dropouts on two treatment groups.

Sensitivity Analyses which alter resolution conditions of primary efficacy analysis will be performed on the ITTI population. Following two endpoints will be assessed as described for the primary efficacy endpoint.

- Time (in days) to resolution of influenza symptom (respiratory and constitutional symptoms)

In the analysis, fever is not considered and the definition of resolution of symptom is the same as those of primary efficacy analysis.

- Time (in days) to resolution of influenza symptom and fever

In the analysis, threshold of resolution of fever is changed to 37.8°C and the definition of resolution of symptom is the same as those of primary efficacy analysis.

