12.9 Suspicious ADE

Subjects will be considered to possibly have ADE if they meet any of the following criteria:

- Symptoms have not resolved or have worsened up to Day 8 after the administration of study drug in the opinion of the investigator
- The subject develops a secondary influenza-like illness after Day 8

Subjects with suspicious ADE will be required to assess virus titer using the nasopharyngeal swab sample, Flu-iiQ™ and body temperature up to Day 8 after the day of ADE occurrence. If symptoms have not resolved or have worsened up to Day 8 after the day of ADE occurrence, same procedures will repeat.

The number and percentage of subjects who meet the criteria for suspicious ADE will be presented by actual treatment group.

Data recorded in 'Suspicious ADE' page of eCRF will be listed in listings for Flu-iiQ™, body temperature and virus titer of nasopharyngeal swab samples which are collected in scheduled visits.

13. Changes to Protocol-Specified Analysis

- The analysis scope for the 1st CSR is extended up to Day 110/EOS for subjects who enrolled in the first season to obtain sufficient data. (currently specified in 8.0 section of the protocol, but updated in 1.1 section of SAP)
- The definition of ITT population is changed to exclude subjects who are screening failures but randomized by accident. (currently specified in 8.4.1 section of the protocol, but updated in 5.3 section of the SAP)
- The definition of safety population is changed to include all subjects who receive any amount of study drug even if it's only the normal saline solution but to analyze such subjects as the placebo group. (currently specified in 8.4.3 section of the protocol, but updated in 5.3 section of the SAP)
- The sensitivity analysis using tipping point analysis will be performed only when there is no censoring case. (currently specified in 8.6.1 section of the protocol, but updated in 10.1 section of the SAP)
- Handling of BLQ values after administration of study drug is updated. (currently specified in 8.5.3 section of the protocol, but updated in 11.1.1 section of the SAP)
- Description of %AUCex is updated according to the European Medicines Agency's guidance in "GUIDELINE ON THE INVESTIGATION OF BIOEQUIVALENCE". (CPMP/QWP/EWP/1401/98 Rev. 1)

CONFIDENTIAL

Statistical Analysis Plan

(CHMP 2010). (currently specified in 8.5.3 section of the protocol, but updated in 11.1.2 section of the SAP)

- Sensitivity analyses of primary efficacy analysis are added.

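### The primary tests leave out both randomisation strata without giving a reason: a low-severity efficiency point, not a validity error

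*SAP*

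**What the plan says.** Both documents stratify the randomisation by the same two factors. Protocol 8.1: "Randomization will be stratified by flu vaccination history within a year (Yes vs No) and participation in PK sub-study (Yes vs No". SAP section 4 repeats it. According to Protocol 5.5, the stratum is also returned with the allocation: "date and time of randomization, and stratum name generated by IWRS will be delivered to the Sponsor".

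The primary analysis uses neither factor. If every subject is followed to resolution, SAP 10.1 compares the groups "using a Wilcoxon rank-sum test to assess differences between treatment groups (CT-P27 45 mg/kg vs placebo, CT-P27 90 mg/kg vs placebo". Under censoring, Protocol 8.5.1 says: "If there is any censoring, the primary efficacy endpoint will be analyzed using Log-rank test, and Kaplan-Meier plots will be presented". The SAP widens this: "the primary efficacy endpoint will be analyzed using Log-rank test and Gehans Wilcoxon test". No stratum or covariate is named for any of these tests.

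The other primary-endpoint analyses do not bring the strata in. SAP 10.1 has a tipping-point analysis and two further analyses, introduced as "Sensitivity Analyses which alter resolution conditions of primary efficacy analysis will be performed on the ITTI population", which drop the fever criterion or relax it. After randomisation, vaccination history returns only as a baseline descriptor (SAP 8.1). No reason for the omission is given.

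**The concern.** A factor is normally made a randomisation stratum because it is thought to matter for outcome. If it does, and allocation is balanced within it, the true variance of the treatment comparison is smaller than an unstratified test assumes. The test then rejects less often than its nominal level under the null, and some power is left unused. With 63 against 38 subjects per comparison and 80% planned power, there is little to spare.

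The choice also has to be made in advance. A stratified test added after the results are known would look selective, whichever way it pointed.

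**Working it through.** **1. The plan's own figure.** Inputs from Protocol 8.1 and SAP 5.2: 63 and 38 evaluable subjects, a difference of 1.8 days, SD 3, two-sided 5%, Wilcoxon test.

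- Standard error = 3 × √(1/63 + 1/38) = 0.616; 1.8/0.616 = 2.921.
- Normal-shift efficiency of the Wilcoxon test is 3/π = 0.955, so the standardised effect is 2.921 × √0.955 = 2.855.
- Power = Φ(2.855 − 1.960) = Φ(0.895) = 81.4%. Direct simulation gives 80.3 to 80.7%.

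The stated 80% is reproduced with an unstratified Wilcoxon test, so the planned test and the sample size agree.

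**2. What a prognostic stratum does.** Let q be the share vaccinated and D the difference in mean recovery time between vaccinated and unvaccinated subjects. Neither is in the documents; both are assumed. With total SD 3, the share of variance due to the stratum is r = q(1−q)D²/9. If allocation is balanced within strata (the block scheme is not stated, so this too is assumed), then approximately:

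- unstratified type I error = 2 × [1 − Φ(1.960/√(1−r))]
- unstratified power = Φ((2.855 − 1.960)/√(1−r))
- stratified power = Φ(2.855/√(1−r) − 1.960)

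| D (days) | q | r | Unstratified type I error | Unstratified power | Stratified power | Change (points) |
|---|---|---|---|---|---|---|
| 1 | 0.3 | 0.21/9 = 2.3% | 4.7% | 81.7% | 82.3% | +0.6 |
| 1 | 0.5 | 0.25/9 = 2.8% | 4.7% | 81.8% | 82.5% | +0.7 |
| 2 | 0.1 | 0.36/9 = 4.0% | 4.5% | 81.9% | 83.0% | +1.0 |
| 2 | 0.3 | 0.84/9 = 9.3% | 4.0% | 82.6% | 85.0% | +2.4 |
| 2 | 0.5 | 1.00/9 = 11.1% | 3.8% | 82.9% | 85.7% | +2.8 |

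The formula ignores the small cost of splitting the sample, so simulation is needed near D = 0.

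**3. Simulation.** 183 randomised, 53 in the PK sub-study, 90% infected, one dose against placebo, normal outcome, total SD 3, effect 1.8 days, PK participation not prognostic; 20,000 trials per scenario. Entries are Wilcoxon power without strata → van Elteren stratified by vaccination.

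| D | q | Balanced within strata (5:5:3 blocks assumed) | Allocation ignoring strata |
|---|---|---|---|
| 0 | 0.3 | 80.7 → 80.2 (−0.5) | 80.9 → 79.9 (−1.0) |
| 1 | 0.3 | 80.7 → 81.0 (+0.3) | 80.8 → 81.1 (+0.3) |
| 1 | 0.5 | 80.2 → 80.7 (+0.5) | 80.7 → 81.0 (+0.3) |
| 2 | 0.3 | 81.3 → 83.7 (+2.4) | 81.2 → 84.1 (+2.9) |
| 2 | 0.5 | 81.4 → 84.2 (+2.8) | 80.6 → 84.5 (+3.9) |

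Unstratified type I error with balanced strata was 5.1% at D = 0, 4.6 to 5.2% at D = 1 and 3.9% at D = 2. With allocation ignoring strata it was 4.7 to 5.1% throughout. The van Elteren test stays at about 5% at D = 2. The Monte Carlo standard error is about 0.3 points for power and 0.15 for type I error, so nothing here exceeds 5% beyond simulation error. A wider set of scenarios (normal and gamma times, SD 3 taken as within-stratum or as total, 20 to 50% vaccinated) gave −1.0 to +1.0 points at D = 1.

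**4. Using all four strata.** At D = 0, q = 0.3, power falls from 80.7 to 79.4% (−1.3) with balanced strata and from 80.9 to 78.6% (−2.3) without. The cells become thin. The expected number of vaccinated placebo subjects in the PK sub-study is 38 × (53/183) × q = 11.0 × q, which is 1.1, 3.3 and 5.5 for q = 0.1, 0.3 and 0.5.

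**The case against.** The strongest reply is that the plan is coherent as it stands. The sample size is stated for a plain Wilcoxon test, both documents specify that test, and neither promises a stratified analysis. Stratifying by vaccination gains about nothing if its effect is a day or less, and costs up to about a point if there is no effect. Recruitment is already described as complete, so replacing a protocol-specified primary test could seem out of proportion.

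Much of this stands. It caps the severity and is why a sensitivity analysis is an acceptable minimum. It does not answer the missing reason, or the fact that the stratum is already held and costs little to use.

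Four stronger readings are tempting, and the documents do not support them.

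- **An undocumented change.** A reader might infer one because SAP section 13 does not mention the strata. That section lists departures from the protocol analysis, and the protocol analysis was unstratified too.
- **A 1-day threshold.** A reader might take the 1-day figure in Protocol 4.2 as the point at which stratifying starts to pay. That figure is the efficacy of available treatment, not the effect of vaccination on recovery.
- **Larger gains under censoring.** A reader might expect these from the log-rank test. Any such figure depends on event times, diary extension and dropout that the documents do not give, so none is claimed.
- **An invalid test.** A reader might infer that omitting the strata invalidates the primary test. Step 3 shows no inflation.

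**Conclusion.** The omission is real and unexplained, but of low severity. A significant result from the planned tests would not be undermined by leaving out the strata, and the sample size need not change. If vaccination history is prognostic and allocation is balanced within strata, the plain Wilcoxon test is mildly conservative: about 4% type I error at an assumed 2-day effect. Stratifying by vaccination moves Wilcoxon power by about −1 to +1 point for effects of 0 to 1 day and by about +1 to +4 points at 2 days.

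These sizes rest on assumed values for the share vaccinated, its effect, the block scheme and the outcome distribution; the documents supply none of them. The statement on type I error is per comparison and concerns the strata only. Testing two doses at 5% each is a separate matter.

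**What to change.** Before unblinding, amend SAP 10.1 and record the change in section 13:

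- Stratify each dose-versus-placebo test by vaccination history as randomised. Use van Elteren if there is no censoring, and stratified log-rank and stratified Gehan tests if there is, with the stratum weights stated.
- Keep the unstratified tests as prespecified sensitivity analyses.
- Leave PK participation out of the main stratification and say why: four strata thin the placebo cells and cost about 1 to 2 points if the factors are not prognostic.

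The minimum alternative is to keep the plain tests as primary and prespecify the stratified versions as sensitivity analyses.

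The cost is SAP wording, the section 13 entry, the titles of the primary tables in SAP 14.7 that name the Wilcoxon test, and programming. No new data are needed. The statistical price of making the stratified test primary is up to about 1 point of Wilcoxon power if vaccination history turns out not to be prognostic.

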1.1 Study Design and Plan

The Statistical Analysis Plan (SAP) is based on the final study protocol CT-P27 2.2 (A Phase IIb, Randomized, Double-blind, Multicenter, Placebo-controlled Study Evaluating the Efficacy and Safety of CT-P27 in Subjects with Acute Uncomplicated Influenza A Infection) Version 5.0 dated 31 January 2018 and electronic Case Report Form (eCRF) Version 4.1 dated 28 September 2017 and covers full study analysis and data presentation. This is a phase IIb, multicenter, placebo-controlled, randomized, double-blind, parallel-arm study to evaluate the efficacy and safety of two doses of CT-P27 (45 mg/kg and 90 mg/kg) in subjects with acute uncomplicated influenza A infection. This proof-of-concept study will provide dose-ranging information for the subsequent clinical development of the drug.

No study procedures will be performed prior to informing the subject about the study and obtaining written informed consent. However, any test result which was obtained within the allowed screening period can be used as screening data for subject's convenience. It is critical that subjects receive treatment with study drug no more than 48 hours after the onset of symptoms (window of +12 hours is allowed). The time of onset of illness is defined as the earlier of either (a) the time when the body temperature was first measured as $\geq 38.0^{\circ}\text{C}$ ($\geq 100.4^{\circ}\text{F}$) or (b) the time when the subject experienced the presence of at least two symptoms that are respiratory and/or constitutional (moderate to severe in intensity). For most subjects, obtainment of the Informed Consent Form (ICF), screening for eligibility, randomization and treatment will occur on the same day. Though obtainment of the ICF may occur on the day prior to screening, randomization or treatment, it must be within 24 hours before the administration of study drug.

To be eligible for enrollment, subjects must have a positive test result for influenza A by a rapid influenza diagnostic test. At screening, nasopharyngeal swab samples will be collected for two times to be used for rapid influenza diagnostic test and virology assessment. The enrollment process is presented in Figure 1.

Figure 1 Enrollment Process

[figure not shown]

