These data will be used to determine the efficacy of treatment with CT-P27 to establish an effect size of CT-P27 in comparison to placebo based on time to resolution of influenza symptoms and fever. Information on effect size, as well as the safety and PK will be used in the selection of doses for subsequent clinical studies.

2. Objectives

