5.2 Determination of Sample Size

This study is designed to obtain effect sizes of 2 different CT-P27 treatment groups and placebo group based on the time from the administration of study drug to resolution of influenza symptoms and fever.

For this proof-of-concept dose-ranging study, assuming 90% of subjects are included in the eligible infected population, the total eligible sample size of 164 (63 eligible infected subjects per CT-P27 treatment groups and 38 subjects in placebo group) achieves 80% power to detect 1.8 days of reduction for the primary endpoint of time to resolution with 5% two-sided significance level and SD of 3 days using a Wilcoxon's rank-sum test.

Considering a dropout rate of 10%, this study will need 183 subjects to be enrolled to achieve 164 evaluable subjects.

For an effect size of 1.5 days of reduction in time to resolution with SD of 2.9 days, the total sample size could be increased to about 250 to achieve at least 80% statistical power with 5% two-sided significance level.

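### The trial is meant to inform dose selection, but no efficacy analysis estimates 90 vs 45 mg/kg with its uncertainty; two p-values against a shared placebo group can split by chance and be misread as a dose difference

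*SAP*

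**What the plan says.** **Purpose.** SAP 1.1 states: "This proof-of-concept study will provide dose-ranging information for the subsequent clinical development of the drug". It adds: "Information on effect size, as well as the safety and PK will be used in the selection of doses for subsequent clinical studies". Protocol 2.2 (Rationale for Current Study) says much the same.

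**Primary analysis.** SAP 10.1 applies a Wilcoxon rank-sum test in the ITTI population "to assess differences between treatment groups (CT-P27 45 mg/kg vs placebo, CT-P27 90 mg/kg vs placebo". The reading rule is: "If p-value is lower than 5%, it is considered that there is a significant difference between placebo and CT-P27". If any subject is censored, log-rank and Gehan-Wilcoxon p-values are given, with quartiles of time to resolution and Kaplan-Meier plots. No estimate of a treatment difference and no confidence interval is specified, either between doses or against placebo.

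**Other efficacy analyses.** SAP 10.2 compares the secondary time-to-event endpoints between placebo and CT-P27 only. The remaining efficacy endpoints are summarised by treatment group. The table list in SAP 14.7 contains no between-dose efficacy contrast, trend test or dose-response model.

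**Between-dose inference.** The only planned analysis of this kind is PK dose proportionality (SAP 11.1.2), which concerns exposure.

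**Sample size.** SAP 5.2 gives "63 eligible infected subjects per CT-P27 treatment groups and 38 subjects in placebo group", a design that "achieves 80% power to detect 1.8 days of reduction" "with 5% two-sided significance level and SD of 3 days using a Wilcoxon's rank-sum test".

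**The concern.** Effect size is a named input to dose selection, yet no output gives the difference in effect between the two doses or how uncertain it is. Whoever selects a dose will have two p-values, both computed against the same placebo group of 38, and a set of per-arm summaries.

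If one p-value is below 5% and the other is not, it is natural to conclude that the first dose works better. That conclusion does not follow, because a significant and a non-significant result against a common control are not a comparison of the two treatments. A split can come from chance alone when the doses are equally effective. Equally, two significant results can conceal a real difference between the doses.

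**Working it through.** **Inputs.** From SAP 5.2: 63, 63 and 38 evaluable subjects; effect 1.8 days; SD 3 days; two-sided 5%; Wilcoxon test. The same section gives an alternative effect of 1.5 days with SD 2.9. Assumptions added here: both doses have the same true effect, times are roughly normal, follow-up is complete, and Wilcoxon efficiency relative to the t-test is 3/π = 0.955. The SAP plans no multiplicity adjustment, so none is applied.

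**Step 1: reproduce the plan's figures.** The mean of each test statistic is

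(d/SD) × √[(63 × 38/101) × 3/π] = 0.6 × √22.63 = 2.855.

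Power = Φ(2.855 − 1.96) = 81.4%. Simulated Wilcoxon tests (20,000 trials) gave 79.9%. The stated 80% reproduces. So does enrolment: 164/0.9 = 182.2, rounded up to 183.

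**Step 2: correlation from the shared placebo group.**

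ρ = (1/38)/(1/38 + 1/63) = 63/101 = 0.624.

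**Step 3: chance that exactly one dose reaches p<0.05.** With equal effects this is 2 × [P(one given dose) − P(both)], where P(both) comes from the bivariate normal with ρ = 0.624.

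| True effect, SD (days) | Each dose | Both | Exactly one |
|---|---|---|---|
| 1.2, 3 | 47.7% | 33.5% | 28.5% |
| 1.5, 3 | 66.2% | 53.2% | 26.0% |
| 1.5, 2.9 | 69.2% | 56.7% | 25.0% |
| 1.8, 3 | 81.4% | 72.2% | 18.6% |
| 2.0, 3 | 88.7% | 82.2% | 13.0% |

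For 1.8 days: 2 × (0.8145 − 0.7215) = 0.186. The value at 1.2 days is close to the maximum. Simulation gave 20.2% at 1.8 days, 26.7% at 1.5 days with SD 3, and 25.3% at 1.5 days with SD 2.9. With skewed (gamma) times it gave 16% at 1.8 days and 26% at 1.5 days.

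**Step 4: what a direct comparison would have shown.** Among the simulated trials with exactly one significant dose, a direct 45 vs 90 mg/kg Wilcoxon test gave p<0.05 in about 13%. The direct contrast would therefore usually have corrected the false impression.

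**Step 5: precision of the missing contrast.** 95% CI half-widths on the mean scale, complete follow-up:

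- 90 vs 45 mg/kg: 1.96 × 3 × √(2/63) = 1.05 days.
- Either dose vs placebo: 1.96 × 3 × √(1/63 + 1/38) = 1.21 days.

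The between-dose contrast is the more precise of the two. It still has 80% power only for a true difference of (1.96 + 0.84) × 3 × √[(2/63)/0.955] ≈ 1.5 days.

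**The case against.** **No rule selects a dose by significance.** A reader might infer from the 5% rule in SAP 10.1 that the dose will be chosen by which test crosses 5%. The documents do not say so. They name effect size, safety and PK, and the 5% rule only defines a significant difference from placebo. This objection stands. The percentages above are the frequency of a misleading pattern, not the error rate of a planned decision.

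**The plan does give dose-specific efficacy.** A reader might also infer that the dose question cannot be addressed at all. That goes too far. Quartiles, Kaplan-Meier plots, symptom scores and viral load are reported by arm. Protocol 2.3 poses only a hypothesis against placebo, and the SAP's tests match it. What the arm summaries lack is the size of the difference between doses with its uncertainty.

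**The size depends on the scenario.** SAP 5.2 pairs the 1.5-day effect with a possible increase to about 250 subjects. In the same allocation, 250 evaluable (about 96/96/58) gives 15.3%, and 250 enrolled with 90% evaluable (about 86/86/52) gives 18.2%. The increase is optional, so the 63/63/38 figures remain relevant.

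**The Wilcoxon branch may not run.** It applies only if every subject is followed to resolution. The scheduled diary ends at Day 8, extended for suspicious ADE, and 10% dropout is assumed, so some censoring is likely. The figures are then approximate. The logic of the shared placebo group also applies to the log-rank and Gehan tests, and the remedy has to work in that branch too.

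**The contrast may not separate the doses.** Its detectable difference of about 1.5 days is close to the whole assumed drug effect of 1.8 days. This stands and is the reason to ask for estimation and not a test. A wide interval would itself be informative.

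**Conclusion.** The gap is real. Dose-ranging is a stated purpose and effect size a stated input to dose selection, but no efficacy estimate of 90 vs 45 mg/kg with its uncertainty is planned. The consequence is a risk of misinterpretation. None of the planned tests against placebo is invalidated.

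At 63/63/38 with equal true effects and unadjusted 5% tests, a split result would occur in about 19% of trials at 1.8 days and about 25–26% at 1.5 days. It peaks near 28.5% around 1.2 days and falls to about 13% at 2.0 days. These figures assume near-normal times and complete follow-up. In a proof-of-concept trial this is an inexpensive improvement that should be made.

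**What to change.** Add to SAP 10.1, before unblinding:

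1. A pre-specified 90 vs 45 mg/kg estimate with 95% CI for time to resolution in the ITTI population, labelled as estimation and not as a confirmatory test.
2. The same measure for each dose against placebo. SAP 10.1 currently defines no effect measure, so one has to be named. It should work with and without censoring, for example the difference in Kaplan-Meier median or in restricted mean time to resolution. A restricted mean also needs its truncation time fixed in advance.
3. A sentence stating that one significant and one non-significant result against placebo will not be read as a difference between doses.

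**Cost.** A short SAP paragraph and extra columns in the primary table, with no new data. An effect scale must be chosen and justified. The between-dose interval may be too wide to separate the doses, at about ±1.05 days on the mean scale with complete follow-up.
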